Adjustments for Multiplicity	24
Interim Analysis	25
General Considerations	25
Subject Populations and Disposition.....	25
Discontinuations	26
Protocol Deviations/Violations.....	26
Data Sets Analyzed	26
Demographic and Other Baseline Characteristics	26
Pre-ecr MEASUREMENT for Visit 3, 4 and 5	27
Medical History And Concomitant Diseases.....	27
Concomitant Medication	27
Study Drug Administration	28
Efficacy Analyses.....	28
Safety Analyses	30
Change to the Planned Analyses.....	33
Appendix 1: Calculations.....	34
Tables, Listings and Figures (TLFs)	34

	Sponsor: Aldeyra Therapeutics, Inc. Sponsor Protocol No. ALDNS2-203-D1
---	---

I. INTRODUCTION

The purpose of the statistical analysis plan (SAP) is to describe the planned analyses and reporting for protocol 18-MO-001:

“An Exploratory Clinical Trial Evaluating Reproxalap Ophthalmic Solutions (0.25% And 0.5%) In Subjects With Seasonal Allergic Conjunctivitis Using The Environmental Exposure Chamber (EEC)”

This SAP is being written with due consideration of the recommendations outlined in the most recent International Council on Harmonization (ICH) E9 Guideline entitled Guidance for Industry: Statistical Principles for Clinical Trials and the most recent ICH E3 Guideline, entitled Guidance for Industry: Structure and Content of Clinical Study Reports (CSR).

This SAP is a summative and definitive plan, based on the final protocol dated November 22, 2018 (Version FINAL 4.0).

The SAP includes details of data handling procedures and statistical methodology. The SAP also outlines the statistical programming specifications for the Tables, Listings and Graphs (TLGs). No interim analysis is planned for this study.

The final statistical analysis will proceed exactly according to the SAP approved by the sponsor as well as by Inflamax Research.

The statistical analysis methods presented in this document will supersede the statistical analysis methods in the clinical protocol. If additional analyses are required to supplement the planned analyses described in the SAP, they will be labeled as post-hoc and will be identified in the CSR.

Responsibilities

Inflamax Research will perform the statistical analyses described herein and is responsible for the production and quality control (QC) of tables, figures, and listings associated with the analyses other than the post hoc analyses.

II. STUDY DESIGN

OVERVIEW OF STUDY DESIGN AND DOSING REGIMEN

ADX-102-AC-011/18-MO0001 is a single center study.

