1. A Visual Analog Scale (VAS) measured on a 0- 100 mm continuous scale where 0 is considered no itching and 100 is considered maximum itch.

[REDACTED]

Sponsor: Aldeyra Therapeutics, Inc.
Sponsor Protocol No. ALDNS2-203-D1

Ocular Tearing

[REDACTED]

[REDACTED]

[REDACTED]

[REDACTED]

[REDACTED]

[REDACTED]

VIII. SAFETY ASSESSMENTS

Safety assessments will include the following:

- Visual Acuity (VA) for Visit 1 through Visit 5.
- Slit Lamp Examination (SLE) for Visit 1 through Visit 5.
- Non-Contact intraocular pressure Tonometry (NCT) during Visit 1 and Visit 3 to Visit 5.
- Dilated Fundus Examination as Screening Visit 1 and Visit 5 and undilated Fundus examination at Visit 2, 3 and 4.
- Vital Signs (VS) for Visit 1 to Visit 5.
- Safety Clinical Laboratory parameters at Screening Visit 1 and at Visit 5.

	
Sponsor: Aldeyra Therapeutics, Inc. Sponsor Protocol No. ALDNS2-203-D1

--	---

- Adverse Events (AEs: reported, elicited and observed) from Visit 2 through Visit 5.

IX. ANALYSIS POPULATIONS

SAFETY POPULATION

All randomized subjects who received at least one dose of IP, regardless of whether clinical trial assessments were performed.

INTENT-TO-TREAT (ITT) POPULATION

All randomized subjects who received at least one dose of IP and have any post-dose assessments. Subjects are evaluated according to the IP treatment of the visit as per the randomized treatment sequence.

COMPLETER POPULATION

COMPLETER population will include all randomized subjects who received IP dosing at all three EEC treatment visit.

PER-PROTOCOL (PP) POPULATION

All ITT subjects will be considered PP if IP dosing occurs and do not have a major deviation from the protocol. The following is a list of protocol violations which would exclude subjects from the PP population:

- Subject did not receive IP as assigned.
- Subject did not meet all inclusion/exclusion criteria.

X. ENDPOINTS

EFFICACY ENDPOINTS

The following efficacy endpoints will be derived for each pharmacodynamic measures in each treatment visit and will be used to assess the activity of Reproxalap Ophthalmic Solutions.

- AUC 0-212 mins for Itching on VAS scale
- AUC 0-212 mins for Itching on 9 points scale
- AUC 0-210 mins for Conjunctival Redness on 9 points scale
- AUC 0-212 mins for Tearing on 4 points scale
- AUC 0-212 mins for TOSS
- AUC 0-92 mins for Itching on VAS scale

	Sponsor: Aldeyra Therapeutics, Inc. Sponsor Protocol No. ALDNS2-203-D1
--	---

- AUC 92-212 mins for Itching on VAS scale

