Data Collected Outside Study Schedule

Data collected at visits that occurred outside the time windows specified in the protocol will be included in the data listings but will not be included in the analyses.

Definition of Baseline

In general, baseline is defined as the last observed measurement prior to the first dose of study medication during Pre-EEC entry at visit (visit 3, visit 4 and visit 5). If patient has more than one non-missing measurement at different time point prior to the first dose, average of these assessment score will be taken to derive the baseline value. The baseline will be used in the change from baseline calculation for each treatment period.

	
Sponsor: Aldeyra Therapeutics, Inc. Sponsor Protocol No. ALDNS2-203-D1

--	---

Derived Variables

- Age is calculated in years after rounding down as follows:
Year of age = (Date [in days format] informed consent signed - Date [in days format] of birth) / 365.25.
- Efficacy assessments will be performed on both eyes. For conjunctival redness, assessments will be made in both temporal and nasal regions. For a symptom and at a specific EEC time point, from the multiple scores observed, the maximum score from both eyes and regions when applicable will represent the worst symptom score and thus will be used for the statistical analysis. This implies that all efficacy summary tables and treatments comparisons will use the maximum observed score at each ECC time points. The Listings of efficacy data however will provide all scores for the eyes and the regions as applicable.

The efficacy endpoints AUC will also be derived using the maximum score at each time point. Similarly, TOSS will be derived using the maximum score at each time point for the ocular itching, conjunctival redness and tearing symptoms.

- TOSS will be derived as the sum total of maximum score from ocular itching, conjunctival redness and tearing symptoms. However, the EEC time points for the ocular itching and tearing symptoms is different from the time points for the conjunctival redness. The scheduled time points for ocular itching will be used to represent the TOSS scheduled time points.

XII. STATISTICAL ANALYSES

MISSING DATA

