Any missing values for the efficacy endpoints for a subject during a visit and a specific time point will be imputed and replaced by the mean value calculated from all non-missing values of the same symptom for the same visit and the time point from all other subjects who has taken the same treatment in that visit.

The imputed missing value for conjunctival redness and itchiness symptoms will be rounded to the nearest 0.5 value in order to match the observed scales. The imputed missing value for tearing symptom will be rounded to the nearest integer value in order to match the observed scale.

ADJUSTMENTS FOR MULTIPLICITY

No multiplicity adjustments will be conducted in this study.

Sponsor: Aldeyra Therapeutics, Inc.
Sponsor Protocol No. ALDNS2-203-D1

INTERIM ANALYSIS

No interim analysis is planned for this study.

GENERAL CONSIDERATIONS

[REDACTED]

[REDACTED]

[REDACTED]

[REDACTED]

[REDACTED]

SUBJECT POPULATIONS AND DISPOSITION

The listing of randomization scheme will be presented with subject identification, sex, age, race, and assignments to the treatment sequence. The following frequencies (number and percent) will be displayed by treatment group and for all subjects combined:

- Subjects Randomized
- Subjects who completed all treatment sessions
- Subjects in the Safety Population
- Subjects in the ITT Population
- Subjects in the COMPLETER Population
- Subjects in the PP Population
- Subjects who withdrew early (total and by reason)

The denominators for the percent calculations will be the number of subjects randomized, whether or not they are included in any of the analyses.

	
Sponsor: Aldeyra Therapeutics, Inc. Sponsor Protocol No. ALDNS2-203-D1

--	---

DISCONTINUATIONS

In the event that any subject is withdrawn or withdraws from the study, a table presenting all subjects withdrawn will be provided. The listing will include subject identifier, visit at withdrawal, time point, treatment ID, and last treatment received prior to withdrawal and the specific reason(s) for withdraw. If a sufficient number of subject withdrawal happens, the frequencies (number and percent) of discontinuations by reason will be presented by last treatment administered and for all subjects combined.

PROTOCOL DEVIATIONS/VIOLATIONS

All deviations including but not limited to study inclusion or exclusion criteria, conduct of the trial, subject management or subject assessment will be listed.

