	
Sponsor: Aldeyra Therapeutics, Inc. Sponsor Protocol No. ALDNS2-203-D1

---	---

[figure not shown]
[figure not shown]
[figure not shown]
[figure not shown]
corresponding electronic CRF along with the reason the medication was taken.

Medications will be coded according to the WHO drug dictionary which includes the WHO Drug Preferred Name and the ATC Classification Level 2 and 4. Prior and concomitant medication data will be listed by subject.

STUDY DRUG ADMINISTRATION

The dosing dates, times during Treatment Visits 3 to 5 will be listed by subject and visit.

EFFICACY ANALYSES

Treatment Comparisons

Sponsor: Aldeyra Therapeutics, Inc.
Sponsor Protocol No. ALDNS2-203-D1

The following 3 contrasts will be evaluated for each primary endpoint:

- Reproxalap Ophthalmic Solution (0.50%) vs. Placebo
- Reproxalap Ophthalmic Solution (0.25%) vs. Placebo
- Reproxalap Ophthalmic Solution (0.50%) vs. Reproxalap Ophthalmic Solution (0.25%)

POST HOC ANALYSIS

1. Additional inferential analysis may be performed whereby additional covariates and other fixed factors may be used in models, depending on the significance of the term and the impact on contrast outcomes.
2. Responder analyses may be performed whereby treatment response may be defined as one and two-point improvements from mean and within-subject baseline and peak scores. In addition to GEE, time to event analyses may also be performed.

[REDACTED]	Sponsor: Aldeyra Therapeutics, Inc. Sponsor Protocol No. ALDNS2-203-D1
------------	---

[REDACTED]

[REDACTED]

[REDACTED]

[REDACTED]

[REDACTED]

SAFETY ANALYSES

All safety data will be analyzed using Safety population.

For safety analysis, summary descriptive statistics such as N, mean, SD, median, minimum and maximum will be provided by treatment group for continuous variables. Frequency distribution as number of subjects and percentage of subjects will be provided for categorical variables. No formal inferential tests will be performed on safety data.

Adverse Events/Adverse Drug Reactions

AEs will be coded using the Medical Dictionary for Regulatory Activities (MedDRA) coding dictionary [REDACTED] preferred term (PT) and system organ classification (SOC). Subjects will multiple events within the same SOC and/or PT are only counted once within the respective frequencies.

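### Filling missing efficacy scores with a rounded group mean makes reported standard errors too small, by about 3–6% for itching if 5% of scores are missing and 7–11% if 10% are

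*SAP*

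**What the plan says.** SAP XII, Missing Data, sets a broad scope: "Any missing values for the efficacy endpoints for a subject during a visit and a specific time point will be imputed". The replacement is a single group mean: the value is "imputed and replaced by the mean value calculated from all non-missing values of the same symptom for the same visit". The donors are matched further and exclude the subject: "and the time point from all other subjects who has taken the same treatment in that visit". Fills for redness and itching are rounded to the nearest 0.5; whether this includes the 0–100 mm VAS is not said. For tearing, "The imputed missing value for tearing symptom will be rounded to the nearest integer value in order to match the observed scale".

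The rule is binding, since SAP I states: "The final statistical analysis will proceed exactly according to the SAP approved by the sponsor". Its effect passes into the endpoints, because SAP XI (Derived Variables) builds the AUCs and TOSS from time-point scores. SAP XII (Treatment Comparisons) adds: "The following 3 contrasts will be evaluated for each primary endpoint". Both documents say there are no primary endpoints, so I read this as the 13 AUC endpoints listed in SAP X. The Protocol Synopsis names a mixed-effects ANCOVA for a three-period crossover.

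Two other rules bear on scope. SAP IX: "COMPLETER population will include all randomized subjects who received IP dosing at all three EEC treatment visit". SAP XI (Data Collected Outside Study Schedule) keeps off-schedule data out of the analyses; it says that data from "visits that occurred outside the time windows specified in the protocol will be included in the data listings but will not be included" there.

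The General Considerations text, parts of the efficacy methods and Appendix 1 (the AUC calculations) are not visible.

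**The concern.** A score filled with its cell mean adds almost no residual variation, yet counts as an observation. The estimated variance falls while the real information also falls, so reported standard errors are too small. The visible text has no multiple imputation, no variance or degrees-of-freedom correction, and no sensitivity analysis that would expose this.

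The rule also discards the best available information. In a crossover, the subject's neighbouring scores and other sessions predict a missing score better than other people do.

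Rounding the fill adds error of its own. On the tearing scale, cell means of 1.4 and 1.6, which differ by 0.2, would be filled as 1 and 2, which differ by 1.

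The COMPLETER population gives no protection: it requires dosing at three visits, not complete scores.

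At stake is the precision claimed for treatment contrasts in a feasibility study, whose variability estimates may guide later trials.

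**Working it through.** **Inputs from the documents.** Three sequences at 1:1:1; about 75 randomised, about 25 per sequence; 60 completers targeted; the fill and rounding rules above. No missing rate, SD or within-subject correlation is given, and the assessment schedule is redacted.

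**Step 1: donors.** Under ABC, BCA and CAB, each treatment at a given visit is taken by exactly one sequence.
- 75/3 = 25 per sequence, which reproduces the plan's figure; 25 − 1 = 24 donors.
- With 60 subjects: 60/3 − 1 = 19 donors.

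**Step 2: closed form.** Let m be the share missing completely at random, n the planned cell size and σ² the relevant variance.
- Reported variance ≈ (1 − m)σ²/n, because filled values add about zero deviation.
- True variance ≈ σ²/[n(1 − m)].
- Reported/true SE ≈ √[(1 − m)²] = 1 − m.
- Actual two-sided error at nominal 0.05 ≈ 2Φ[−1.96(1 − m)].

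| m | SE ratio | Actual error |
|---|---|---|
| 0.02 | 0.98 | 0.055 |
| 0.05 | 0.95 | 0.063 |
| 0.10 | 0.90 | 0.078 |

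**Step 3: simulation with scattered gaps.** Assumptions: 75 subjects, 12 or 14 time points, gaps at random, SAP rounding, AUC per session, and a crossover model with subject, period and treatment. Setting A includes a baseline covariate, 12 times and within-subject correlation 0.3–0.85; its ranges also cover tearing. Setting B includes a baseline covariate, 14 times and a between-subject variance share of 0.2–0.6. Setting C has 12 times and no baseline covariate. B and C are shown for itching (VAS and 9-point). Entries are reported/true SE.

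| Missing | A | B | C |
|---|---|---|---|
| 2% | 0.98–0.99 | 0.97–0.98 | 0.98–0.99 |
| 5% | 0.95–0.97 | 0.94–0.95 | 0.95–0.96 |
| 10% | 0.90–0.93 | 0.89–0.90 | 0.89–0.92 |

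The shortfall for itching is therefore about 2%, 3–6% and 7–11%. In setting A, coverage of 95% intervals was 94.4–95.0%, 93.6–94.6% and 92.2–93.6%.

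**Step 4: is the fill the cause?** In setting A, interpolating the subject's own scores gave ratios of 0.99–1.02 and coverage of 94.6–95.5% at all three rates. A separate REML check without rounding gave 0.939 (5% missing) and 0.892 (10%) under the group-mean fill, against 1.006 and 0.994 with no imputation.

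**Step 5: tearing.** The result depends on where the cell mean lies.
- Setting B gave shortfalls of 7.3% at 5% missing and 13.2% at 10%.
- With the means assumed in setting A, rounding moved the ratio by at most 0.012 at 5% and 0.02 at 10%.
- In extreme cases at 10% missing, the ratio was about 0.99 with the mean on an integer and about 0.81 with it at a rounding boundary: a shortfall of about 1% to 19%. At 5% missing the range is about 1% to 10%.

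**The case against.** **Little may be missing.** This is one centre, with scores captured on an electronic tablet and doses given by staff. The analysed score is the maximum over both eyes (and regions, for redness), so one missing eye need not create a gap. SAP VI says discontinuation ran below expectation. With 12 assumed times there are 36 scores over three sessions, so 5% means about 1.8 missed scores per subject and 10% about 3.6. This stands: at 2% missing the point is negligible.

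**The consequence is modest.** In setting A, 5% missing costs at most about 1.4 points of coverage (95 − 93.6). The trial has no formal hypotheses, and 13 endpoints × 3 contrasts = 39 comparisons are unadjusted. This also stands, and it limits the severity. It does not make the standard errors right.

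**A correction may sit in text that is not visible.** This cannot be excluded. The SAP's precision table is also generic: it sets decimal places for standard errors, confidence intervals and p-values without promising them for each contrast.

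Stronger readings that a reader might infer are not supported:
- *Whole missed sessions are filled.* The scope wording could be stretched that far. But the rule speaks of a time point within a visit and of others on the same treatment at that visit, which presupposes attendance. Out-of-window visits are separately excluded.
- *The fill biases the treatment difference through symptom-driven early exit.* This needs exit rates by treatment, and the documents give none.
- *The planned dropout sets the missing rate.* 1 − 60/75 = 20% is a planning figure for subjects, not a rate of missing scores.
- *One range fits every scale.* Step 5 shows that it does not fit tearing.

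**Conclusion.** The rule is a real flaw as written: single group-mean imputation, rounded, ignoring the subject's own data. If filled values are analysed as observed, reported standard errors for itching with scattered gaps are too small by about 2% at 2% missing, 3–6% at 5% and 7–11% at 10%. For tearing, the shortfall is about 1–10% at 5% and 1–19% at 10%, depending on how near the cell mean lies to a rounding boundary.

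These figures rest on assumed missing rates, an assumed schedule and correlation, and gaps unrelated to the scores. The harm is overstated precision in any intervals and p-values reported, not a failed confirmatory test. Minor to moderate; worth fixing because it is cheap. Confidence is medium, given what is not visible.

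**What to change.** In the main analysis, replace the rounded group-mean fill with these rules:

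- **Bracketed gap.** Where the same subject has observed scores on both sides within the session, and the gap does not span the second dose (about 95 minutes) or chamber exit (about 215 minutes), derive the AUC by linear interpolation.
- **Other gap in an attended session.** Use multiple imputation conditional on the subject's own scores, treatment, period and baseline, without rounding. Add a sensitivity analysis that leaves the session missing.
- **Session not attended, or excluded as outside the window.** State that it stays missing and is handled by the planned mixed-effects crossover model.
- **Reporting.** Give counts of missing time points by treatment and visit. The SAP already plans to summarise missed visits and assessments by deviation type if numbers suffice.

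The cost is SAP wording and modest programming, with no new data. With interpolation, reported standard errors become about 2–4% larger at 5% missing and 5–9% larger at 10%. If little is missing, little changes.

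Separately, the return windows need reconciling. The Protocol Synopsis gives two weeks ± 3 days for Visit 4. Protocol 3.1 and SAP II give a minimum of two weeks for Visit 4, and a minimum of two weeks with ± 3 days for Visit 5. The schedule table is not visible. The windows decide which visits the SAP excludes.

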pemphigoid, significant conjunctival scarring, chemical burn, herpetic or neurotrophic keratitis, Cryopyrin Associated Periodic Syndrome (CAPS), or keratoconus;

[REDACTED]

[REDACTED]

Statistical Analysis:

Approximately 150 subjects with ragweed-induced, moderate-to-severe allergic conjunctivitis will be screened in the EEC in order to randomize approximately 75 subjects, and for 60 subjects to complete the study. Approximately twenty-five (25) subjects will be assigned to each of three (3) treatment sequences, ABC, BCA, and CAB. While not based on formal power considerations, 60 subjects completed is sufficient to produce reasonably reliable statistical conclusions based on the following:

[REDACTED]

Prior to database lock, the Sponsor will finalize a statistical analysis plan (SAP) that will detail all planned analyses. Any analyses conducted in addition to those specified in the SAP will be clearly documented as post hoc.

In brief, the efficacy analyses of all efficacy endpoints will be carried out in the Intent-to-Treat (ITT) population. Supportive analyses may also be provided for Itching endpoint(s) using the Per-Protocol (PP) population.

Descriptive statistics of all activity endpoints as well individual data listings will be presented by treatment group and efficacy measures. For each efficacy endpoints, treatment comparisons will be made between Reproxalap Ophthalmic Solutions (0.25% and 0.5%) and vehicle. The treatment comparison will be performed using a mixed-effects Analysis of Covariance Model (ANCOVA) for a crossover study for 3 periods.

[REDACTED]

The endpoints that will be analyzed are the following:

AUC 0-212 mins for Itching on VAS scale
AUC 0-212 mins for Itching on 9 points scale
AUC 0-210 mins for Conjunctival Redness on 9 points scale
AUC 0-212 mins for Tearing on 4 points scale
AUC 0-212 mins for TOSS
AUC 0-92 mins for Itching on VAS scale
AUC 92-212 mins for Itching on VAS scale
AUC 0-32 mins for Itching assessed by VAS Scale
AUC 32-72 mins for Itching assessed by VAS Scale
All 0 time-point measurements will be pre-EEC entry/ baseline values. All the time-points are approximate values

Additional Exploratory Analyses

In addition, descriptive statistics including Change from Baseline (CFB) for each treatment and each post-EEC time-point may be derived and used as exploratory efficacy endpoints to evaluate the efficacy of Reproxalap Ophthalmic Solutions (0.25% and 0.5%). Other exploratory analyses may be added post-hoc.

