2.2 Clinical Trial Assessments and Endpoints

The clinical trial is exploratory in nature to the safety, tolerability, and pharmacodynamic activity of Reproxalap Ophthalmic Solutions (0.25% and 0.5%) compared to Vehicle Ophthalmic Solution in subjects with allergic conjunctivitis in an EEC model. There are no primary endpoints and no formal statistical hypotheses.

The assessments used in this trial include ocular itching self-assessed by each subject using two scales, a Visual Analog Scale (VAS) and a 9-point scale.

VAS is measured on a 0-100 mm continuous scale where 0 is considered no itching and 100 is considered maximum itch.

[figure not shown]
[figure not shown]

Figure 3. Photographic Ocular Redness

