At Treatment EEC Session Three (Visit 5), all procedures performed at Visit 4 will be repeated except that each subject will be given a different treatment dependent on the treatment sequence the subject was randomized to [Reproxalap Ophthalmic Solution (0.25%) (Treatment A), Reproxalap Ophthalmic Solution (0.5%) (Treatment B), or Vehicle Ophthalmic Solution (Treatment C)]. At the end of the visit, a urine pregnancy test will be administered to WOCBP. Subjects will undergo ophthalmic examinations (Snellen VA, SLE, NCT, and a dilated fundus examination), clinical safety lab tests and vital signs will be collected to ensure safety prior to exit of the clinical trial.

	
Sponsor: Aldeyra Therapeutics, Inc. Sponsor Protocol No. ALDNS2-203-D1

---	---

Table1. Schedule of Events and Assessments

Sponsor: Aldeyra Therapeutics, Inc.
Sponsor Protocol No. ALDNS2-203-D1

[figure not shown]
	
Sponsor: Aldeyra Therapeutics, Inc. Sponsor Protocol No. ALDNS2-203-D1

---	---

Table 2. Schedule of Staff-Assessed Conjunctival Redness Recording

[figure not shown]
[figure not shown]

--

Table 3. Schedule of Subject Assessed Itching and Tearing

	
Sponsor: Aldeyra Therapeutics, Inc. Sponsor Protocol No. ALDNS2-203-D1

--	---

Table 4. Schedule of Staff-Assessed Conjunctival Redness Recording Post-EEC Exit

[figure not shown]
[figure not shown]

Table 5. Schedule of Subject Assessed Itching and Tearing Post-EEC Exit

	
Sponsor: Aldeyra Therapeutics, Inc. Sponsor Protocol No. ALDNS2-203-D1

---	---

III. INVESTIGATIONAL TREATMENT

Reproxalap Ophthalmic Solutions (0.25% and 0.5%) and Vehicle Ophthalmic Solution are supplied as sealed Investigational Product (IP) kits, please refer to the current protocol for further.

IV. STUDY OBJECTIVES

- To evaluate the feasibility of using the EEC clinical trial design to assess the activity of Reproxalap Ophthalmic Solutions (0.25% and 0.5%) in an allergic conjunctivitis population.
- To assess safety, tolerability, and pharmacodynamic activity of Reproxalap Ophthalmic Solutions (0.25% and 0.5%) compared to Vehicle Ophthalmic Solution in the treatment of seasonal allergic conjunctivitis in subjects allergic to ragweed using the EEC with exposure to airborne ragweed pollen.

V. DETERMINATION OF SAMPLE SIZE

VI. Randomization and Masking

Eligible subjects will be randomized 1:1:1 to one of three treatment sequences of ABC, BCA, CAB, where:

- Treatment A: Reproxalap Ophthalmic Solution (0.25%)

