If numbers are sufficient, protocol deviations will be summarized (number and percent of subjects) by type of deviation. The protocol deviations will be grouped into different categories which may include, but are not limited to:

- Missed visit
- Inclusion/Exclusion criteria
- Missed procedures/assessments
- Informed consent
- Documentation
- Study drug administration
- Safety
- Lack of compliance

DATA SETS ANALYZED

A listing of subjects excluded from the Safety, ITT, COMPLETER and PP populations will be produced.

DEMOGRAPHIC AND OTHER BASELINE CHARACTERISTICS

Demographic data and baseline characteristics will be listed by subject and summarized by Analysis Populations using standard summary statistics.

- Gender, Ethnicity and Race

	
Sponsor: Aldeyra Therapeutics, Inc. Sponsor Protocol No. ALDNS2-203-D1

--	---

- Age (years), height (cm), weight (kg) and BMI (kg/m²)
- Systolic blood pressure (mm Hg)
- Diastolic blood pressure (mm Hg)
- Heart rate (beats/minute)
- Pulse rate (beats/min)
- Respiratory rate (breaths/minute)
- Medical History
- Skin Prick Test

Unless stated otherwise, percentages will be calculated out of the number of patients in the given Analysis Set.

PRE-EEC MEASUREMENT FOR VISIT 3, 4 AND 5

Summary statistics of following pre-EEC measurement at Visit 3 to Visit 5 will be tabulated by treatment, visit and eye.

- Fundus exam
- Snellen VA
- NCT
- SLE
- Subject rating of ocular itching and tearing
- Staff grading of conjunctival redness

MEDICAL HISTORY AND CONCOMITANT DISEASES.

Description of medical history and concomitant disease findings prior to screening will be coded using Medical Dictionary for Regulatory Activities (MedDRA) version 20.0 or higher.

Medications will be coded according to the WHO drug dictionary which includes the WHO Drug Preferred Name and the ATC Classification Level 2 and 4. Prior and concomitant medication data will be listed by subject.

A disease or illness reported at Screening reported as medical history without a start date will be included in medical history without a date assigned. Medical history will be sorted by descending overall frequency, by SOC and PT in the summary table. Medical history data listings will be sorted by treatment, patient number, start date, SOC and PT.

CONCOMITANT MEDICATION

Concomitant medication, prescription or over-the-counter will be defined as, taken within 30 days prior to Visit 1 through to Visit 5, is to be recorded on the source document and

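### SAP Post Hoc item 1 lets the treatment contrast help choose the model that then tests it, and no readable text requires every fitted model to be shown

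*SAP*

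**What the plan says.** Under Efficacy Analyses, the SAP lists three treatment contrasts: each concentration against vehicle, and 0.5% against 0.25%. Post Hoc Analysis item 1 follows. It begins "Additional inferential analysis may be performed whereby" and continues: "additional covariates and other fixed factors may be used in models, depending on the significance of the term and the impact on contrast outcomes".

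Several other provisions set the context:

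- **Planned model.** The Protocol Synopsis (Statistical Analysis) says: "The treatment comparison will be performed using a mixed-effects Analysis of Covariance Model (ANCOVA) for a crossover study for 3 periods". The terms of that model are not visible.
- **Labelling.** SAP section I says of supplementary analyses that "they will be labeled as post-hoc and will be identified in the CSR". The Synopsis and Protocol sections 10.1 and 10.4 likewise require analyses beyond the SAP to be documented as post hoc.
- **Inferential status.** Protocol 2.2: "There are no primary endpoints and no formal statistical hypotheses". SAP, Adjustments for Multiplicity: "No multiplicity adjustments will be conducted in this study".
- **Possible covariates.** The SAP's list of pre-EEC measurements at Visits 3 to 5 includes "Subject rating of ocular itching and tearing" and staff grading of conjunctival redness.
- **Sequences.** SAP section VI: subjects are "randomized 1:1:1 to one of three treatment sequences of ABC, BCA, CAB".

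Text is redacted under General Considerations in SAP section XII and directly after the post hoc items.

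**The concern.** The second criterion in item 1 is the effect on the treatment contrasts. A p-value or interval has its stated error rate only if the model was not chosen by looking at the quantity being tested. If several models are fitted and the one with the more favourable contrast is kept, the reported p-value is too small and the interval covers too seldom.

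The post hoc label tells the reader that the analysis was unplanned. It does not say how many models were tried or that the contrast guided the choice. In a trial without a primary endpoint, readers rely on estimates and intervals, and a selected model could appear in the study report as support for activity. This is a stated rule that works badly, not merely a missing detail.

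**Working it through.** The documents state no alpha, power or error rate for these models, so there is no plan figure to reproduce. The check asks what the rule does to the error rate when there is no treatment effect.

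**Inputs from the documents.** Sequences ABC, BCA, CAB; three periods; target 60 completers; contrast 0.5% versus vehicle.

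**Inputs assumed, because the documents do not give them.** Two-sided 5% test; complete data; fixed subject, period and treatment effects; K independent session-level covariates, each with within-subject correlation r with the outcome. The variance explained is K × r². For K = 3 this is 3 × 0.2² = 12% at r = 0.2 and 3 × 0.3² = 27% at r = 0.3.

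**Which terms can matter.** With complete data, a covariate that is constant within a subject (age, sex) cancels from the within-subject contrast. Only terms that vary by session can move it, such as the pre-EEC ratings. Some of these may already be in the planned ANCOVA.

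**Null simulation, K = 3, 60 completers, 10,000 replicates.** Rejection rate in %, nominal 5. The planned model gave 4.6 to 5.3 across all scenarios. The first two rules keep the model with the smallest contrast p-value over all subsets of covariates. The third adds a term if it moves the contrast by more than 10% in either direction.

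| r | Smallest p, any subset | Smallest p, added terms all p < 0.05 | Direction-neutral 10% rule |
|---|---|---|---|
| 0 | 5.7 | 4.8 | 4.8 |
| 0.1 | 6.6 | 5.7 | 5.0 |
| 0.2 | 8.5 | 7.9 | 5.0 |
| 0.3 | 10.7 | 10.6 | 4.0 |

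Monte Carlo 95% error near 10% is 1.96 × √(0.10 × 0.90 / 10,000) = 0.6 points. A separate run gave 10.0 and 9.9 for the first two rules at r = 0.3. A two-sided rate of 10% means that a nominal 95% interval from the kept model covers about 100 − 10 = 90%.

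**False pro-drug results only (nominal 2.5%).** Smallest p, no significance condition, K = 3: 3.5% at r = 0.1 and 4.9% at r = 0.3. These are about half the two-sided rates, because roughly half of the two-sided rejections favour vehicle.

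**What larger figures require.** The documents name none of the other fixed factors, so carryover is only an assumed example. In these sequences 0.5% always follows 0.25%, vehicle always follows 0.5%, and 0.25% always follows vehicle. With within-subject variance σ² and n subjects, the contrast variance is 2σ²/n without first-order carryover and 10σ²/n with it. At n = 60 that is 0.033σ² and 0.167σ², a ratio of 5, so such a term can move the contrast a good deal. The smallest-p rates at 60 completers are:

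- Carryover alone: 8.9% (6.6% if it must be significant).
- Five covariates at r = 0.3, explaining 5 × 0.3² = 45% of within-subject variance: 17.7%.
- Those five covariates plus carryover: 29.4%.

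**If only term significance guides selection.** The rates are 4.7 to 6.0% with covariates only and 5.7 to 7.3% with carryover also optional. Some inflation can therefore remain after the contrast criterion is removed.

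**The case against.** The strongest reply is that item 1 does not say favourable models will be kept. It can be read as a neutral check on whether adjustment changes the contrast. Under the direction-neutral 10% rule the rates stay near nominal: 3.4 to 5.6% with covariates only and 4.7 to 5.8% with carryover optional. This stands, and it is why the concern is conditional. One qualification applies: keeping the single model that moves the contrast most in either direction gives 4.6 to 5.9% with covariates only, but up to 16.2% when carryover is a candidate.

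Item 1 also joins its two criteria, so rates without the significance condition overstate its literal reading. That stands too. For covariates correlated with the outcome, however, the condition protects little: 10.6% against 10.7% at r = 0.3. For carryover alone it helps more.

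The models are optional, labelled post hoc and tied to no formal hypothesis. This limits the consequence, but a label neither restores the error rate nor requires every fitted model to be tabulated.

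A reader might infer that the SAP plans to pick results favourable to the drug, or that error rates near 18% or 30% are to be expected. The documents support neither. They give no direction and name no candidate terms, and those figures need favourable selection plus five strong covariates, with carryover as well for the higher one. The plan also has a washout of about two weeks between sessions. Nor can one conclude that no reporting rule exists, because the redacted blocks might contain one.

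**Conclusion.** The point holds as a minor defect in a stated rule. Item 1 allows the contrast to influence the choice of the model that tests it, and the readable text does not require all fitted models to be shown. If favourable models are kept, under the assumed conditions (60 completers, three session-level covariates, r = 0.2 to 0.3, added terms significant) the two-sided error is about 8 to 10% instead of 5%. The false pro-drug rate without the significance condition is about 3.5 to 5% instead of 2.5%, for r = 0.1 to 0.3. With the direction-neutral threshold rule it is close to nominal. The size depends on the number and strength of the candidate terms, which the documents do not give. The planned crossover ANCOVA is not affected.

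**What to change.** In Post Hoc item 1:

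1. Delete the effect on the treatment contrasts as a criterion for using a term.
2. Require every fitted post hoc model to be reported (terms, contrast, interval) beside the planned ANCOVA as a sensitivity estimate. Any change in the contrast is then shown and not used for selection. If carryover is tried, show results with and without it.

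The second step is the core of the fix, because the first leaves selection on term significance in place. Full reporting also keeps the legitimate question of whether adjustment changes the contrast. Naming candidate session-level covariates before unmasking is optional. If the redacted text already contains these requirements, a cross-reference in item 1 is enough.

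The cost is SAP wording, slightly less post hoc flexibility and a few more table rows.
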